9.4 Procedures at each visit and during treatment periods

9.4.1 Screening visit

During the screening visit the investigator explains to the participant the aims of the study, the study procedures, the drug under investigation and potential risks (see also chapter 3.7 risks and benefits). Written informed consent will be obtained from all participants without limiting time for signature. Participants who are candidates for enrolment into the study will be evaluated for eligibility during the screening visits by the investigator (inclusion, exclusion criteria). Screening visit will take place within 2 weeks before first test visit and consists of

- Assessment of personal and family history
- Psychosocial assessment
- Assessment of medication history
- Physical examination

The following questionnaires will be used to assess psychiatric disorders:

- Depressive symptoms will be assessed with the self-rating questionnaire MADRS-S based on the MADRS (Schmidtke, 1988). This scale consists of 9 items assessing subjects' mood, feelings of unease, sleep, appetite, ability to concentrate, initiative, emotional involvement, pessimism and zest for life. Each item is scored between 0 and 3. The total score is calculated by summing the answers of the nine items, ranging between 0 and 27 (higher scores indicate increased impairment). A score of ≥ 8 results in exclusion. In case of suicidal tendency (Item 9 > 1), the subject is excluded and advised to consult a psychologist/psychiatrist. We will provide subjects with addresses.
- Self-assessment questionnaire covering mental health, drug and alcohol consumption, sleeping habits and some sociodemographic information.

The investigator decides, whether there are contraindications for the administration of study medication.

The medical examination performed covers:

Vital signs (blood pressure / heart rate) will be taken with the participant having been in a seated position for at least 5 minutes.

- Height / weight (for calculation of BMI)
- Physical examination; findings will be recorded as “normal” or “abnormal”.
- Twelve lead ECG with formal readings (Wilson, Einthoven, Goldberger), device: Schiller AT10, will be taken and rated by a specialist familiar with the study medication at the Phase I Research Unit (PRU) University Hospital Basel (see contract with PRU).
- Venous blood samples (2,7 ml and 4,7 ml) will be taken at the Phase I Research Unit University Hospital Basel to measure:

- Blood count (incl. platelets) / hemoglobin / hematocrit
- Blood chemistry including: sodium, potassium, chloride, calcium, phosphate, creatinine, uric acid, bilirubin, alkaline phosphatase, LDH, AST, ALT, GGT, pancreatic amylase, albumin, total protein (+Alb./Glob.), C-reactive protein, creatine kinase.

Laboratory values outside the reference range of the laboratory and considered clinically relevant will lead to exclusion of the subject from study participation.

Blood samples will be analyzed by the laboratory of University Hospital Basel. Blood samples will be discarded directly after analysis.

Clinically significant abnormal ECG readings will result in exclusion of the subject.

Resting Motor Threshold (rMT) will be determined as described in chapter 9.2.2. During screening a handedness questionnaire (short version of Edinburgh Handedness Inventory (EHI)) will be administered, as rMT will be measured at the dominant hand.

All female of childbearing potential will be requested to use adequate contraception starting 10 days before each intervention period and during intervention period, such as an oral, injectable, or implantable contraceptive or contraceptive devices (IUP). To minimize the risk of exposure to IMP we will perform a pregnancy test before administration of study drug on test day 1 and 3.

Screening failures equal to participants not meeting all inclusion criteria or meeting one or more of the exclusion criteria. Excluded participants will be listed on a screening failure log. The whole screening will be repeated if the wash out period (time between test day 2 and 3) lasts more than 26 days.

9.4.2 Test days (visits 2-5)

At the beginning of the test days 1 and 3, all female participants will perform a pregnancy test. Pregnancy test will be performed in a urine sample according to instructions of Axaclear, Axapharm. Axaclear is a one-step hCG (monoclonal anti-hCG antibodies) urine pregnancy test used for qualitative (visual) determination of hCG in urine specimen for early detection of pregnancy. The pregnancy tests will be stored with IMP at the same conditions. Additionally women will be requested again to use an adequate contraception during the wash-out period.

There will be a short examination consisting of vital signs, assessment of concomitant medication, sleep duration, self-assessment questionnaire covering drugs and alcohol consumption and adverse events.

Intake of study medication will take place at the same time point for each subject. We will provide a continental breakfast to be eaten 2 hours after intake of study medication. The breakfast consists of two rolls, butter and jam. After breakfast study participants will be provided with fruits and crackers (e.g. Darvida). Whole day water and herbal and fruit tea (no green or black tea) will be available. Caffeine containing beverages are only allowed during breakfast.

Testing will take place at the same time for each subject to minimize the influence of diurnal differences in cognitive test performance.

There will be a 4-h waiting period allowing the medication to reach high cerebrospinal fluid concentration.

After this time period, the cognitive test battery will be administered. A parallel version of the test battery will be administered on each test day.

For the duration of the different study parts see table 1 (Duration of Study parts, page 12).

At the end of each test day, participants will be asked about their actual wellbeing. If there are no complaints / symptoms they will be dismissed. In case of minor health problems the participant will have to stay in the study center until recovery under medical control. In case of more severe incidents staff will act according to chapter 10.

Assessments in participants who prematurely stop the study: There will be a final examination after withdrawal during test days for whatever reason. The examination consists of recording adverse events and assessing vital signs.

The study including assessment of inclusion and exclusion criteria (other than laboratory parameters and ECG that will be assessed at the Phase I Research Unit of the University Hospital Basel), medication intake and assessment of study outcomes will be conducted at the Transfaculty Research Platform Molecular and Cognitive Neurosciences, University of Basel.

9.4.3 *Treatment periods*

During the visits 2 and 4 (test days 1 and 3) every subject will be supplied with a plastic container containing the remaining 6 tablets of IP to be taken twice per day during the following 3 days, the first tablet in the evening of visit 1 (resp. 3) and the last tablet in the morning of the visits 3 and 5 (test days 2 and 4). Each subject receives a total of 7 verum tablets and 7 placebo tablets.

During the treatment days, the participants document the intake of the tablets and – if any – adverse events via a separate personal login directly in secuTrial® (s. chapter 8.4, Compliance with study intervention).

10 SAFETY

10.1 Definitions

10.1.1 Adverse Event (AE)

An Adverse Event (AE) is any untoward medical occurrence in a patient or a clinical investigation participant administered a pharmaceutical product and which does not necessarily have a causal relationship with the study procedure. An adverse event can therefore be any unfavorable and unintended sign (including an abnormal laboratory finding), symptom, or disease temporally associated with the use of a medicinal investigational product, whether or not related to the medicinal investigational product.

In this study, the following very common AEs being already described in the prescribing information Fampyra® (version from May 2019) are excluded from recording, but will be measured as possible confounding factor using VAS:

- headache
- gastrointestinal disturbances such as dyspepsia, abdominal pain, constipation and nausea
- dizziness

All other clinically relevant AEs will be fully recorded by describing the AE, time of onset, duration and resolution, assessment of intensity, relationship to study drug and measures taken

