Description		Screening		Test day 1	P/V or V/P	Test day 2	Wash-out period	Test day 3	V/P or P/V
Day		within 14 days before Visit 2		1		4		12-30	Test day 4
Screening									
• Written informed consent, assignment of the subject number									
• Personal, family and medication history									
• Self-assessment mental health and sleeping habits, MADRS-S, EHI									
• Physical examination									
• ECG, Blood sample									
Treatment periods									
• Electronic intake diary									
• Electronic AE diary (VAS headache, gastrointestinal discomfort, dizziness; free text)	3.5 days				x				x
Wash-out period (8-82 days between V3 and V4)	8-82 days						x		
Test days									
Pre-examination test days									
• Vital signs									
• Flu-like symptoms, common cold symptoms									
• Pregnancy test (Visits 2 and 4)									
• Questionnaire drugs and alcohol consumption during last 3 days resp. past 12 hours									
• Sleep duration last 24 hours									
• AE recording									
• VAS headache, gastrointestinal discomfort, dizziness; VAS tiredness, motivation									
Assignment of the randomization number	5 min		x						
Intake of study medication	5 min		x	x	x		x	x	x
Waiting time (incl. continental breakfast 2 hours after intake of study medication)	4 h		x		x		x		x
Before start of testing									
• AE recording									
• VAS headache, gastrointestinal discomfort, dizziness; VAS tiredness, motivation	15 min		x		x		x		x
Testing Phase – part 1									
• n-Back			x		x		x		x
• Processing speed task SDMT	45 min								
• Digit Span									
Break	15 min		x		x		x		x
Testing Phase – part 2									
• BOMAT	15 min		x		x		x		x
rMT measurement using TMS	15 min	x			x				x
Final Examination									
• AE recording									
• VAS headache, gastrointestinal discomfort, dizziness; VAS tiredness, motivation	15-20 min		x		x		x		x

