7.4 Criteria for withdrawal / discontinuation of participants

Participants have the right to withdraw from the study at any time for any reason without being obliged to give reason. There will be a final examination after withdrawal for whatever reason. The investigator also has the right to withdraw participants from the study if it is in the best interest of the participant.

The following reasons result in withdrawal:

- Adverse events challenging the health of the participant if continuing the study
- Adverse events prohibiting cognitive testing or rMT-measurement, e.g.
 - headache, dizziness and nausea more than mild or
 - having slept less than 4 hours during the last night (Visits 3 and 5).
- Participant being ill at ease during rMT measuring
- Intake of psychoactive substances within 3 days before test days (e.g. benzodiazepines, antidepressants, neuroleptics, cannabis)
- Non-Compliance
- Severe protocol violations
- Administrative troubles
- Positive pregnancy test (test day 1 or test day 3)

- Alcohol intake within 12 hours before start of all visits

Withdrawal date and reason will be listed in the participant enrolment log. Safety data will be analyzed for all participants, who received at least one dose of study medication. There will be no anonymization of the data. For information about data handling see chapter 12.3.

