9.3 Assessment of safety outcomes

The following known side effects will be recorded using visual analog scales: headache, gastrointestinal discomfort, dizziness

Adverse events: All clinically relevant (S)AEs occurring after the participant has signed the informed consent until follow up visit will be fully recorded in the participants eCRF. Description of (S)AE, time of onset, duration and resolution. Assessment of intensity, relationship to study drug and measures taken. For documentation of (S)AEs see section 10.

Laboratory parameters: No laboratory parameters will be assessed after screening.

Vital signs: Vital signs (BP, HR) will be taken as described in screening procedures. Blood pressure and heart rate will be used as baseline before intake of study medication, during waiting period, before testing and before end of visit to control for side effects of the medication.

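### Section 10.1.1 exempts headache, GI disturbances and dizziness from AE recording at any severity, so a non-serious case that is more than mild or ends participation has no clear requirement for a grade and causality entry

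*Combined protocol and SAP*

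**What the plan says.** Section 10.1.1 lists headache, gastrointestinal disturbances (an open list that includes nausea) and dizziness as already described in the prescribing information. It states that they "are excluded from recording, but will be measured as possible confounding factor using VAS". Full recording is for the rest: "All other clinically relevant AEs will be fully recorded by describing the AE, time of onset, duration and resolution", followed by intensity, relationship to study drug and measures taken.

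Section 7.4 treats the same symptoms as adverse events that can end participation, giving "headache, dizziness and nausea more than mild" as an example. What it then requires is that "Withdrawal date and reason will be listed in the participant enrolment log".

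Section 9.3 assigns the three symptoms to VAS. In its next paragraph it asks for full recording of every clinically relevant (S)AE, and then says "For documentation of (S)AEs see section 10". Section 9.4.2 describes the examination after withdrawal: "The examination consists of recording adverse events and assessing vital signs". It does not name the VAS. The study schedule does, under Final Examination: "VAS headache, gastrointestinal discomfort, dizziness; VAS tiredness, motivation".

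The safety objective in section 4.4 names the incidence of these side effects and, as a separate element, the rate of AEs. Section 11.4.5 gives only the safety population, which is everyone who received a dose.

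**The concern.** Section 3.7 names four AE types as the most frequent: dizziness, headache, insomnia and gastrointestinal discomfort. Three of the four fall under the exemption, and it has no upper severity limit. Followed as written, the AE rate in section 4.4 leaves out non-serious moderate or severe cases of these symptoms, including cases that end participation.

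The VAS gives a within-subject comparison of drug and placebo. It does not give a graded, causality-assessed count of the cases that stopped someone taking part. Efficacy is analysed per protocol in completers, with drop-outs replaced (section 11.4.1), so the safety record is where withdrawn cases should be counted clearly.

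**Working it through.** The plan gives no figure of its own on this point. The check is mainly a reading of the sections against each other, with three small calculations.

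**1. Does any section restore an AE entry for a non-serious case?**
- Section 10.1.1 sets no limit by grade or consequence.
- Section 5.3 lists the three symptoms apart from AE recording and refers back to 10.1.1.
- Section 9.3 has a broad rule on clinically relevant AEs, but sends these symptoms to VAS and defers to section 10, where the exemption sits.
- Section 9.4.2 asks for adverse events to be recorded after withdrawal, without saying whether the exempt symptoms count.
- Sections 7.4 and 11.4.1 ask for the date, the reason and a description of drop-outs, but not for a grade or causality category.
- Sections 10.1.4, 10.3.1 and 10.4.1 cover all SAEs with no carve-out, so serious cases are documented and assessed.

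No section clearly restores the entry. Sections 9.3 and 9.4.2 could be read as doing so.

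**2. What is captured anyway?** The schedule lists the symptom VAS at three points on each test day (pre-examination, before testing, final examination). There are four test days, so 3 × 4 = 12 sets per completer, plus the electronic diary with VAS and free text in both treatment periods.

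Section 10.3.2 lists six AE fields. For a non-serious withdrawal case:

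| Field | Other source |
|---|---|
| Onset | VAS and diary, approximately |
| Duration | VAS and diary, approximately |
| Resolution | Follow-up under 8.5 and 10.4.6 |
| Action | Enrolment log (7.4); concomitant medication (8.6, 8.7) |
| Intensity on the 10.2.2 scale | Partial: see step 3 |
| Relationship to study treatment | None |

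Four of the six fields have another source, one is partly covered and one has none.

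**3. How much of the grade is lost?** A section 7.4 withdrawal for headache, dizziness or nausea rests on the judgement that the symptom is more than mild, and the reason is logged. The case is therefore known to lie above grade 1. Life-threatening and fatal cases (grades 4 and 5) are SAEs under section 10.1.2. What remains unknown is grade 2 versus grade 3. Two kinds of case fall outside this inference: a more-than-mild case that does not lead to withdrawal, and a withdrawal for another gastrointestinal symptom, which the section 7.4 example does not name. No VAS cut-off for mild is given.

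**4. How many withdrawals might be affected?** Section 3.7 reports no discontinuations due to AEs in healthy subjects, either after a single 10 mg dose or after 5 days of 10 mg twice daily. It gives 47 subjects for the 5-day dosing. Assume that all 47 are the denominator. With 0 events in n, the one-sided 95% upper bound is 1 − 0.05^(1/n):
- 1 − 0.05^(1/47) = 0.062, or 6.2%
- 44 × 0.062 = 2.7 participants

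The range is 0 to about 3 of 44. It is a rough guide, because section 7.4 may be stricter than whatever led to discontinuation in that study, and because replacement of drop-outs means that more than 44 may be dosed.

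**The case against.** The split between VAS symptoms and AEs is deliberate and disclosed. Section 4.4 names symptom incidence and AE rate as two elements, and sections 5.3 and 9.3 follow that division. In a double-blind placebo crossover, repeated VAS ratings within each person are good evidence on tolerability, arguably better than individual causality judgements. This stands for common mild symptoms, and the exemption should be kept there. It does not cover the case that ends participation, where a graded and assessed entry is what a reader of the AE table will expect.

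A reader might infer that serious cases go unrecorded, or that withdrawals for these symptoms leave no trace. The documents support neither: the SAE route has no exemption, and the withdrawal reason, follow-up, VAS and diary all remain. A reader might also infer that sections 7.4 and 10.1.1 contradict each other. They do not: one governs participation and the other governs recording. Nor do the documents show that the withdrawal examination omits the VAS. Both 7.4 and 9.4.2 call it a final examination, and the schedule's Final Examination lists the VAS.

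Timing also counts. Version 7 is dated 05/04/2022 and the first participant was planned for 09/2021. On those dates, a change made now would put two recording rules into one trial. That is a real cost, and the report must disclose it.

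**Conclusion.** The point holds in a limited form. For non-serious headache, gastrointestinal disturbance or dizziness that is more than mild or leads to withdrawal, the plan does not clearly require a severity grade and a causality assessment. The AE rate in section 4.4 omits these cases, although the symptoms are assessed separately by VAS. For withdrawals due to headache, dizziness or nausea, the loss comes down to moderate versus severe and individual causality.

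Few withdrawals are likely: at most about 3 of 44 by the rough bound, which assumes a denominator of 47 and a comparable threshold for stopping. The documents give no frequency for more-than-mild cases that do not lead to withdrawal, so their number cannot be stated. The primary outcome, SAE capture and follow-up are not affected. Priority: minor, cheap improvement.

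**What to change.** Change documentation only; the withdrawal rule in section 7.4 stays as it is.

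- **10.1.1:** limit the exemption to non-serious cases that are mild on the section 10.2.2 scale and do not lead to withdrawal. Require the section 10.3.2 fields for all other cases of these symptoms.
- **9.3:** cross-refer to that rule.
- **11.4.5:** report AEs by treatment beside the VAS results. State that mild cases of these symptoms that do not lead to withdrawal are captured by VAS only. If the rule changes after enrolment began, state which participants fall under which rule.
- **9.4.2 (optional):** confirm that the withdrawal examination is the schedule's Final Examination, which already lists the VAS.

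No concomitant-medication trigger is needed, because that treatment is already recorded under 8.6 and 8.7. The AE log, the grading scale and the VAS already exist. The cost is a few extra log entries, and each symptom will be split between the AE log and the VAS, which the 11.4.5 wording has to explain.

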10.1.2 Serious Adverse Event (SAE)

A Serious Adverse Event (SAE) is classified as any untoward medical occurrence that:

- results in death,
- is life-threatening,
- requires in-patient hospitalization or prolongation of existing hospitalization,
- results in persistent or significant disability/incapacity, or
- is a congenital anomaly/birth defect.

In addition, important medical events that may not be immediately life-threatening or result in death, or require hospitalization, but may jeopardize the patient or may require intervention to prevent one of the other outcomes listed above should also usually be considered serious. (ICH E2A)

SAEs should be followed until resolution or stabilization. Participants with ongoing SAEs at study termination (including safety visit) will be further followed up until recovery or until stabilization of the disease after termination.

10.1.3 Unexpected Adverse Drug Reaction

An “unexpected” adverse drug reaction is an adverse reaction, the nature or severity of which is not consistent with the applicable product information (e.g. investigator’s brochure for drugs that are not yet approved and prescribing information for approved drugs, respectively). (ICH E2A)

10.1.4 Suspected Unexpected Serious Adverse Reactions (SUSARs)

The Sponsor-Investigator evaluates any SAE that has been reported regarding seriousness, causality and expectedness. If the event is related to the investigational product and is both serious and unexpected, it is classified as a SUSAR. In order to determine a SUSAR unblinding is needed.

10.2 Assessment of (Serious) Adverse Events and other safety related events

10.2.1 Assessment of causality

Both Investigator and Sponsor-investigator make a causality assessment of the event to the study drug, based on the criteria listed in the ICH E2A guidelines:

Relationship	Description
Definitely	Temporal relationship Improvement after dechallenge* Recurrence after rechallenge (or other proof of drug cause)
Probably	Temporal relationship Improvement after dechallenge No other cause evident
Possibly	Temporal relationship Other cause possible
Unlikely	Any assessable reaction that does not fulfil the above conditions
Not related	Causal relationship can be ruled out

*Improvement after dechallenge (stop administering a drug, to see whether its suspected effects cease to occur) only taken into consideration, if applicable to reaction

